#### **4.2.2 Testing for common *EGFR* mutations**

Only participants with NSCLC with common *EGFR* mutations of ex19del and L858R will be eligible for inclusion in the study. A patient can be considered eligible for the study on the basis of documented *EGFR*m through any of ARMS, Super-ARMS, NGS analysis from accredited laboratories.

For patients eligible for inclusion in the study based on the pre-existing common *EGFR*m plasma and/or tissue sample results, the local *EGFR* tissue testing laboratory methods will be recorded in the respective electronic case report forms (eCRF).

#### **4.3 End of Study Definition**

The end of the study is defined as the date of the scheduled visit of the last participant in the study shown in the SoA in the study.

The study is expected to start participant enrolment at in Q1 2022 and to end by Q1 2024.

The study may be terminated at individual centres if the study procedures are not being performed according to GCP, or if recruitment is slow. Depend on the determination of the study team. If the site is no patients enrol lasts for 3 months from the site initiation, it will be defined as slow recruitment.

A participant is considered to have completed the study if he/she has completed all phases of the study including the scheduled procedure shown in the SoA.

The study may be stopped if, in the judgment of AstraZeneca, study participants are placed at undue risk because of clinically significant findings.

## **5 STUDY POPULATION**

The target population of interest in this study is participants with locally advanced or metastatic

NSCLC, harbouring common *EGFR*m of ex19del/L858R and having evidence of disease progression following 1L Osimertinib.

Prospective approval of protocol deviations to recruitment and enrolment criteria, also known as protocol waivers or exemptions, is not permitted.

Each subject should must meet all of the inclusion criteria and none of the exclusion criteria for this study. Under no circumstances can there be exceptions to this rule. Participants who do not meet the eligibility criteria requirements are screen failures; refer to Section 5.4.

## **5.1 Inclusion Criteria**

Participants are eligible to be included in the study only if all of the following criteria apply:

### **Informed Consent**

- 1 Capable of giving signed informed consent, which includes compliance with the requirements and restrictions listed in the informed consent form (ICF) and in this protocol.
- 2 Provision of signed and dated, written informed consent form prior to any mandatory study-specific procedures, sampling, and analyses.

The ICF process is described in Appendix A3.,

### **Sex and Age**

- 3 Male or female, age at least 18 years.

### **Type of Participant and Disease Characteristics**

- 4 Pathologically confirmed non-small cell lung cancer (NSCLC) with documented *EGFR* sensitive mutation (*EGFR* 19del and L858R) positive before Osimertinib 1L.
- 5 Locally advanced (clinical stage IIIB, IIIC) or metastatic NSCLC (clinical stage IVA or IVB) or recurrent NSCLC (per Version 8 of the International Association for the Study of Lung Cancer [IASLC] Staging Manual in Thoracic Oncology), not amenable to curative or radiotherapy (e.g., this may occur as systemic recurrence after prior surgery for early stage disease or patients may be newly diagnosed with stage IIIB/IV disease, which is at the start of Osimertinib therapy).
- 6 Patients must have been treated with Osimertinib as first line therapy until disease progression. Evidence of disease progression following 1L Osimertinib can be confirmed by investigators with criteria in Response Evaluation Criteria in Solid Tumours (RECIST) Version 1.1.
- 7 Agree to provide adequate tissue and whole blood for testing after disease progression following 1L Osimertinib.

## **Reproduction**

- 8 Female participants who are not abstinent (in line with the preferred and usual lifestyle choice of the participant) and intend to be sexually active with a male partner must be using highly effective contraceptive measures, must not be breast feeding, and must have a negative pregnancy test prior to the enrolment or must have evidence of non-child-bearing potential by fulfilling 1 of the following criteria at screening:
  - Post-menopausal, defined as more than 50 years of age and amenorrhoeic for at least 12 months following cessation of all exogenous hormonal treatments
  - Women under 50 years old would be considered as postmenopausal if they have been amenorrhoeic for 12 months or more following cessation of exogenous hormonal treatments and have luteinizing hormone (LH) and follicle-stimulating hormone (FSH) levels in the post-menopausal range for the institution
  - Documentation of irreversible surgical sterilization by hysterectomy, bilateral oophorectomy or bilateral salpingectomy but not tubal ligation.

Further information is available in Appendix E (Definition of Women of Childbearing Potential and Acceptable Contraceptive Methods).

- 9 Male participants must be willing to use barrier contraception.

## **5.2 Exclusion Criteria**

Participants are excluded from the study if any of the following criteria apply:

### **Medical Conditions**

- 1 Any concurrent and/or other active malignancy that may affect tissue or whole blood testing results.
- 2 As judged by the investigator, any evidence of severe or uncontrolled systemic diseases, which in the investigator's opinion, makes it undesirable for the participant to participate in the study or that would jeopardise compliance with the protocol,. Screening for chronic conditions is not required.

### **Prior/Concomitant Therapy**

- 3 Any concurrent anticancer treatment except local radiotherapy and radiotherapy for CNS metastasis. Concurrent use of hormonal therapy for non-cancer-related conditions (eg, hormone replacement therapy) is allowed.

4

### **Prior/Concurrent Clinical Study Experience**

- 5 Judgment by the investigator that the patient should not participate in the study if the patient is unlikely to comply with study procedures, restrictions and requirements.

### **Other Exclusions**

- 6 Involvement in the planning and/or conduct of the study (applies to both AstraZeneca staff and/or staff at the study site).
- 7 In addition, the following are considered criteria for exclusion from the exploratory genetic research:
  - Prior allogeneic bone marrow transplant
  - Non-leukocyte depleted whole blood transfusion within 120 days of genetic sample collection.

### **5.3 Lifestyle Considerations**

- 1 Female participants of child-bearing potential who are not abstinent (in line with the preferred and usual lifestyle choice of the participant) and intend to be sexually active with a male partner must use acceptable methods of contraception from screening until at least 6 weeks after discontinuing study treatment.
- 2 Male participants must use barrier contraceptives (condoms) during sex with a female partner of child-bearing potential (including a pregnant partner) from the time of screening throughout the completion of the study.

Participants must follow the contraception requirements outlined in Appendix E.

### **5.4 Screen Failures**

Screen failures are defined as participants who consent to participate in the clinical study but are not subsequently entered in the study. A minimal set of screen failure information is required to ensure transparent reporting of screen failure participants to meet the Consolidated Standards of Reporting Trials publishing requirements and to respond to queries from regulatory authorities. Minimal information includes demography, screen failure details, eligibility criteria.

### **5.5 Procedures for handling incorrectly enrolled patients**

Patients who fail to meet the eligibility criteria should not, under any circumstances, be enrolled. There can be no exceptions to this rule. Where a patient does not meet all the eligibility criteria but is enrolled in error, the Investigator should inform the AstraZeneca Study Physician immediately, and a discussion should occur between the AstraZeneca Study Physician and the Investigator regarding whether to continue or discontinue the patient from the study. The Study Physician should ensure all decisions are appropriately documented. The Investigator should make documentation in the medical record as appropriate.

## **6 PARTICIPANT DISCONTINUATION/WITHDRAWAL**

### **6.1 Participant Withdrawal from the Study**

- A participant may withdraw from the study at any time at his/her own request, or may be withdrawn at any time at the discretion of the investigator for behavioural, compliance, or administrative reasons. This is expected to be uncommon.
- At the time of withdrawal from the study, if possible, an Early Study Intervention Discontinuation visit should be conducted, as shown in the SoA. See SoA for data to be collected at the time of study withdrawal and for any further evaluations that need to be completed.
- If the participant withdraws consent for disclosure of future information, the sponsor may retain and continue to use any data collected before such a withdrawal of consent.
- If a participant withdraws from the study, it should be confirmed if he/she is still agrees for existing samples to be used in line with the original consent. If he/she requests withdrawal of consent for use of samples, destruction of any samples taken and not tested should be carried in line with what was stated in the informed consent and local regulation. The investigator must document the decision on use of existing samples in the site study records and inform the Global Study Team.

### **6.2 Lost to Follow-up**

A participant will be considered lost to follow-up if he or she repeatedly fails to return for scheduled visits and no contact has been established by the time the study is completed (see Section 4.3), such that there is insufficient information to determine the participant's status at that time.

Participants who decline to continue participation in the study should be documented as "withdrawal of consent" rather than "lost to follow-up." Investigators should document attempts to re-establish contact with missing participants throughout the study period. If contact with a missing participant is re-established, the participant should not be considered lost to follow-up and evaluations should resume according to the protocol.

The following actions must be taken if a participant fails to return to the clinic for a required study visit:

- The site must attempt to contact the participant and reschedule the missed visit as soon as possible and counsel the participant on the importance of maintaining the assigned visit schedule and ascertain whether or not the participant wishes to and/or should continue in the study.
- Before a participant is deemed lost to follow-up, the investigator or designee must make every effort to regain contact with the participant (where possible, 3 telephone calls and, if

necessary, a certified letter to the participant's last known mailing address or local equivalent methods). These contact attempts should be documented in the participant's medical record.

Discontinuation of specific sites or of the study as a whole are handled as part of Appendix A.

## **7 STUDY ASSESSMENTS AND PROCEDURES**

Study procedures and their timing are summarized in the SoA. Data collection following study analysis until the end of the study is described below.

- Protocol waivers or exemptions are not allowed.
- Immediate safety concerns should be discussed with the sponsor immediately upon occurrence or awareness to determine if the participant should continue or discontinue study intervention.
- Adherence to the study design requirements, including those specified in the SoA, is essential and required for study conduct.
- All screening evaluations must be completed and reviewed to confirm that potential participants meet all eligibility criteria. The investigator will maintain a screening log to record details of all participants screened and to confirm eligibility or record reasons for screening failure, as applicable.
- Procedures conducted as part of the participant's routine clinical management (eg, blood count) and obtained before signing of the ICF may be utilised for screening or baseline purposes provided the procedures met the protocol-specified criteria and were performed within the time frame defined in the SoA.

### **7.1 Enrolment/screening period**

At screening, consenting patients are assessed to ensure that they meet eligibility criteria. Patients who do not meet these criteria must not be enrolled into the study.

The following will be performed at screening:

#### **Written informed consent**

Each potential patient will provide written informed consent prior to starting any study specific procedures.

All patients will be required to consent for collection of a tumor sample and a plasma sample after disease progressed during 1L Osimertinib. This consent is included in the main patient informed consent form (ICF).

#### **Assignment of patient screening number**

As per standard, enrolment number(E-code) is assigned to the patient and Principle Investigator or delegate should perform enrolment/screening call.

### **Collect clinical information**

Demographic data and other characteristics will be recorded and will include date of birth or age, gender, race and/or ethnicity, and smoking history, *EGFR* mutation type, histology, clinical stage with lymph node and distant metastasis at diagnosis and post 1L Osimertinib, ECOG/WHO performance status through electronic medical record or information follow-up. A standard medical and surgical history will be obtained. Duration of 1L Osimertinib treatment, best response of 1L Osimertinib and progression pattern post 1L Osimertinib, will be collected for analysing the correlation between gene profile post 1L Osimertinib and effect of Osimertinib 1L treatment.

## **7.2 General Assessments**

### **7.2.1 Physical Examinations**

Physical examination will be performed and include assessments of the following; general appearance, skin, head and neck (including ears, eyes, nose and throat), respiratory, cardiovascular, abdomen, lymph nodes, thyroid, musculoskeletal (including spine and extremities) and neurological systems.

Physical examination, weight, height will be measured during screening only.

### **7.2.2 WHO/ECOG Performance Status**

WHO/ECOG performance status will be assessed at the times specified in the SoA based on the following:

- 0 Fully active; able to carry out all usual activities without restrictions.
- 1 Restricted in strenuous activity, but ambulatory and able to carry out light work or work of a sedentary nature (eg, light housework or office work).
- 2 Ambulatory and capable of self-care, but unable to carry out any work activities; up and about more than 50% of waking hours.
- 3 Capable of only limited self-care; confined to bed or chair more than 50% of waking hours.
- 4 Completely disabled; unable to carry out any self-care and totally confined to bed or chair.
- 5 Dead.

## **7.3 Biomarker research**

Instructions for the collection, handling, storage and shipping of biological samples will be provided in the study-specific laboratory manual, Appendix B and Appendix C. Samples should be stored in a secure storage space with adequate measures to protect confidentiality.

Samples will be destroyed at end of the study (as defined in the protocol) in line with consent and local requirements.

- Samples collected in China will be stored and disposed of according to local laws and regulations during the study.
- Remaining sample aliquots will be destroyed following completion of the study.

For further details on Handling of Human Biological Samples, see Appendix B.

### **7.3.1 Collection of Samples for Gene Profile Analysis**

The subject's consent to the use of donated biological samples for research is mandatory at disease progression following 1L Osimertinib in the SoA Samples will be collected from all participants and be used for detecting gene alteration and pathological transformation to explore the whole gene profile post Osimertinib 1L treatment for guiding subsequent treatment strategy.

A unstained, archival tumor tissue sample from a fresh biopsy tissue in a quantity sufficient to allow for gene profile at the time of screening will be collected. Tissue samples will be used for the extraction and analysis of deoxyribonucleic acid (DNA). For the requirement of tissue sample and plasma sample, refer to appendix F.

Whole blood samples (approx. 2\*10 mL) will be taken at disease progression post Osimertinib 1L treatment in the SoA (Table 1). Blood samples to generate plasma samples will be collected from all participants. These samples will be used for the extraction and analysis of circulating tumour deoxyribonucleic acid (ctDNA).

Genetic profiles in tissue and plasma will be analyzed by the central lab NGS testing and then used to analysis positive percentage agreement, sensitivity/specificity of plasma to evaluate concordance between plasma and tissue for exploring whether plasma can be substitute for tissue when patients cannot accept tissue biopsy. The analytical method will be used is described in Section 8.3.2.

### **7.3.2 Other Study Related Biomarker Assessments**

Already collected tissue samples may be analysed on different biomarkers thought to play a role in protocol-specific rationale including, but not limited to, tissue biomarkers of SCLC by IHC to evaluate pathology transformation. Biomarkers of SCLC include, but not limited to, CD56, Syn, CgA, TTF-1, CK, Ki-67 and CAM5.2, which is the routine testing in the clinical practice. The analytical method will be used is described in Section 8.3.2.

In the case of sufficient tissue samples, these collected tissue samples may be analyzed on the prevalence of MET amplification and MET overexpression; the concordance of MET amplification between FISH in tissue samples and ddPCR in blood samples; the overlap ratio

of prevalence between MET amplification by FISH and MET overexpression by MET IHC.

The MET amplification testing by FISH in tissue samples and by ddPCR in blood samples (approx. 10 mL) will be tested in central lab.

MET overexpression by MET IHC testing in tissue samples will be tested in the pathology department of local sites.

The detailed analytical method will be used is described in Section 8.3.2.2.3.

### **7.3.3 Storage and destruction of samples**

The processes adopted for the coding and storage of samples for genetic analysis are important to maintain subject confidentiality. Sample storage and destruction will be performed according to the central labs' policy and China HGR regulations. DNA is a finite resource that may be used up during experiments. The results of any further analyses will be reported either in the Clinical Study Report itself or as an addendum, or separately in a scientific report or publication.

All genetic testing and analysis will be performed after China HGR approval. Mutation testing residual samples collected will be destroyed.

For further details on Handling of Human Biological Samples, including storage, re-use and destruction, refer to Appendix B and the Laboratory Manual.

## **8 STATISTICAL CONSIDERATIONS**

Statistical analyses will be performed by AstraZeneca or its representatives. A comprehensive SAP will be prepared with final amendments completed prior to database lock.

There is a potential selection biases in this study. Selection bias: the patients who are eligible and consent to participate in the current study will be enrolled consecutively and without personal preference.

### **8.1 Sample Size Determination**

Approximately 200 participants will be enrolled to achieve NGS and IHC testing.

Assuming some common gene alteration with an incidence of 20%, then with 200 subjects the 95% CI will be around 14.7% - 26.2% based on an exact method (Clopper-Pearson).

Table below summarizes the 95% CIs for the target incidences ranging from 10% to 50% with sample size of 200.

Assumed incidence of gene mutation	95% CIs
10%	6.2%, 15.0%
20%	14.7%, 26.2%
30%	23.7%, 36.9%
40%	33.2%, 47.1%
50%	42.9%, 57.1%

In addition, 200 subjects are enough to have 86% probability to observe at least one case if the incidence of an gene alteration is 1%.

**Note:** “Enrolled” means a participant’s, or their legally acceptable representative’s, agreement to participate in a clinical study following completion of the informed consent process. Potential participants who are screened for the purpose of determining eligibility for the study, but are not enrolled in the study, are considered “screen failures”, unless otherwise specified by the protocol.

Assuming a potential dropout rate for loss to follow-up of 10%, the number to be accrued will be 180.

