### **Number of Participants:**

Approximately 200 participants in *EGFR*m locally advanced or metastatic NSCLC with the evidence of disease progression following 1L Osimertinib will be enrolled and 15 sites will be involved to elucidate the gene profile in paired tissue and plasma so that approximately 180 participants whom would be get gene profile, assuming a 10% drop-out.

**Note:** "Enrolled" means a participant's, or their legally acceptable representative's, agreement to participate in a clinical study following completion of the informed consent process. Potential participants who are screened for the purpose of determining eligibility for the study, but are not randomly assigned/assigned in the study, are considered "screen failures", unless otherwise specified by the protocol.

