Note: The screening visit will confirm that the patients will be receiving a biopsy (scheduled for after enrolment), but they will not actually receive a biopsy at the screening visit.  
CSP=Clinical Study Protocol; ECOG=Eastern Cooperative Oncology Group; ICF=informed consent form; WHO=World Health Organisation

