### **8.3.2 Biomarker analysis**

#### **8.3.2.1 Primary Endpoint**

To evaluate the potential molecular resistance mechanism by tissue analysis at disease progression post 1L Osimertinib treatment, tissue samples will be collected at the disease progression. And then the gene profiling of molecular alterations including but not limited to mutations in, amplifications, deletion, fusion and expression of relevant pathway gene will be explored by NGS analysis.

The primary objective is to describe the gene profile in *EGFR*m advanced NSCLC Patients after progression on 1L osimertinib treatment.

Gene profile in tissue will be analysed by NGS method. All gene alterations(e.g., gene mutation, amplification, deletion, fusion, etc.) and histological transformation detected will be observed. Proportion of Gene X alteration(%) = (number of patients with Gene X, which is an example of a certain gene)/(total number of patients in the FAS)×100%. Some cases which patients have more than one gene alteration need to be considered.

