5. ANALYSIS METHODS

5.1 General Aspects

All statistical analyses will be completed using SAS version 9.4 or later, and R 4.0 or later. Descriptive statistics will be provided for all variables, as appropriate. Continuous variables will be summarized by the number of observations, mean, standard deviation, median, interquartile range (Q1, Q3), minimum, and maximum. Categorical variables will be summarized by frequency counts and percentages for each category. The 95% confidence interval (CI) will be calculated as appropriate.

The analyses will be based on Full analysis set (FAS), which will include all patients who meet the required inclusion/exclusion criteria and have valid Gene data from both plasma and tissue.

Patients missing tissue or plasma NGS data or MET data will not be used for concordance analysis, but only for individual tissue or plasma analysis.

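### The sample-size precision and detection figures assume 200 analysed patients, but the plan expects about 180, and Protocol 8.1 calls that 180 the number to be accrued

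*Protocol*

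**What the plan says.** Protocol 8.1 opens with about 200 participants to be enrolled. For an alteration with 20% incidence it states: "then with 200 subjects the 95% CI will be around 14.7% - 26.2% based on an exact method (Clopper-Pearson". It continues: "Table below summarizes the 95% CIs for the target incidences ranging from 10% to 50% with sample size of 200". It adds that "200 subjects are enough to have 86% probability to observe at least one case" when the incidence is 1%. SAP 2.2 repeats the same table and statements.

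The synopsis (Number of Participants) and SAP 2.2 both say about 200 will be enrolled "so that approximately 180 participants whom would be get gene profile, assuming a 10% drop-out". The last sentence of Protocol 8.1 puts the same arithmetic differently: "Assuming a potential dropout rate for loss to follow-up of 10%, the number to be accrued will be 180". SAP 2.2 does not contain that sentence.

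For the primary endpoint, Protocol 8.3.2.1 divides the number of patients with an alteration by the "total number of patients in the FAS", and SAP 5.4.1 does the same. The FAS (Protocol Table 3, SAP 3.1) requires eligibility and valid gene data from both plasma and tissue.

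**The concern.** There are two linked problems.

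- **The n behind the figures.** The plan allows for a 10% loss and then leaves it out of the only calculations that support the sample size. Those calculations should describe the denominator expected in the analysis, which is the FAS, not the number who sign consent.
- **The label on 180.** Protocol 8.1 gives 200 to be enrolled at its start and 180 to be accrued at its end. Read literally, these are two recruitment targets. If 180 were accrued and 10% then lost, 162 would remain.

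What is at stake is whether the stated precision and rare-alteration detection are what the design can be expected to deliver. No hypothesis test depends on it.

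**Working it through.** **Inputs**

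- Enrolled: about 200 (Protocol synopsis, 4.1 and 8.1; SAP 2.2).
- Loss: 10% (same synopsis paragraph, Protocol 8.1, SAP 2.2).
- Interval: two-sided 95% Clopper-Pearson (Protocol 8.1, SAP 2.2).
- Denominator: FAS (Protocol 8.3.2.1, SAP 5.4.1).

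**Step 1: which number is which.** 200 × (1 − 0.10) = 180, and 180 / (1 − 0.10) = 200. So 200 is the number to enrol and 180 is the number left after loss. The synopsis and SAP 2.2 have this right; the last sentence of Protocol 8.1 does not.

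**Step 2: reproduce the plan, then repeat at 180.** With x = n × p, the lower limit is the 2.5% quantile of Beta(x, n − x + 1) and the upper limit is the 97.5% quantile of Beta(x + 1, n − x).

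| Incidence | Stated (n = 200) | Recomputed, n = 200 | Recomputed, n = 180 | Width, 200 → 180 |
|---|---|---|---|---|
| 10% | 6.2–15.0 | 6.22–15.02 | 6.04–15.34 | 8.81 → 9.31 |
| 20% | 14.7–26.2 | 14.69–26.22 | 14.42–26.60 | 11.53 → 12.18 |
| 30% | 23.7–36.9 | 23.74–36.86 | 23.41–37.26 | 13.13 → 13.86 |
| 40% | 33.2–47.1 | 33.15–47.15 | 32.78–47.55 | 13.99 → 14.77 |
| 50% | 42.9–57.1 | 42.87–57.13 | 42.47–57.53 | 14.27 → 15.06 |

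The stated table is reproduced at n = 200 to within rounding. At n = 180 each limit moves outward by 0.18 to 0.40 points. Total widths grow by 0.5 to 0.8 points, which is 5.5% to 5.7% in relative terms.

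**Step 3: detection of a 1% alteration.** P(at least one case) = 1 − 0.99^n.

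- n = 200: 86.6% (printed as 86%).
- n = 180: 83.6%, which is 3.0 points below the recomputed figure and 2.4 below the printed one.
- n needed for 86%: ln(0.14) / ln(0.99) = 195.6, so 196 patients with results.

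**Step 4: if 8.1 were taken literally.** 180 accrued × 0.9 = 162, and 1 − 0.99^162 = 80.4%.

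**Step 5: the alternative denominator.** SAP 5.1 says patients missing one sample type are left out of the concordance analysis "but only for individual tissue or plasma analysis". On that reading the tissue n could lie between 180 and 200. Taking 190 as an assumed midpoint (x = 38 at 20%), the interval is 14.6 to 26.4 and detection is 85.2%. Reaching 200 would require every patient in the 10% loss to have a valid tissue result.

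**The case against.** The strongest reply is that nothing is miscalculated. Every figure is openly tied to 200 subjects, the interval is introduced as approximate, and SAP 2.2 gives the 180 just before the table, so a reader can make the adjustment. This is correct, and the point is not one of faulty computation. But disclosing n = 200 does not make it the expected analysis n.

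A second reply is that SAP 5.1 keeps single-sample patients for the tissue-only and plasma-only summaries. That may raise the tissue n above 180, but the written formulas still divide by the FAS. A patient lost before any sampling enters neither summary, and such losses are possible: the note to the Schedule of Activities says patients "will be receiving a biopsy (scheduled for after enrolment". So 200 remains the best case, not the expected one.

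A third reply concerns the remedy. The documents attribute the 10% to drop-out or loss to follow-up and do not say that it also covers ineligibility or failed sequencing. If those losses come on top, the FAS falls below 180 and even the restated figures would be slightly generous. This objection stands to the extent that the 10% total must be labelled an assumption.

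Finally, the effect is small and the accrual wording is one sentence, contradicted by the opening of its own section. Both are true and are reflected in the weight given here.

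**Conclusion.** Both parts hold, and the point is minor. The confidence intervals and the detection probability are right for 200 patients but describe a larger denominator than the roughly 180 the plan expects. The cost in precision is at most 0.4 points per limit, and the chance of seeing a 1% alteration is about 84%, not 86%. Separately, Protocol 8.1 attaches the accrual label to the post-loss number.

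This rests on the plan's own 10% loss being the total loss between enrolment and the FAS, and on the FAS being the denominator, as the formulas state. If single-sample patients are counted for tissue, the figures fall between those at 180 and those at 200. If ineligibility and assay failure are additional to the 10%, they are somewhat worse than at 180. In neither case does a test, a power claim or a precision target in the visible text change.

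**What to change.** In Protocol 8.1 and SAP 2.2, restate the table at the expected FAS of 180:

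- 10%: 6.0 to 15.3
- 20%: 14.4 to 26.6 (also in the sentence above the table)
- 30%: 23.4 to 37.3
- 40%: 32.8 to 47.6
- 50%: 42.5 to 57.5

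Change the detection statement to about 84% with 180 patients.

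Replace the last sentence of Protocol 8.1 with: about 200 participants will be enrolled so that about 180 are in the FAS, assuming that 10% are lost for any reason (including drop-out before sampling, ineligibility, or invalid tissue or plasma NGS). Present the 10% total explicitly as an assumption.

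If the SAP 5.1 rule is kept, add that the n for tissue-only or plasma-only frequencies may lie between 180 and 200, and align the denominators in the formulas with that rule.

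The cost is editorial: the table, the 20% interval and the 1% statement in both documents, one sentence in Protocol 8.1, and possibly a note on SAP 5.1 with matching denominators. It needs no extra patients and no change to enrolment; only aligning the denominators would settle which n the tissue and plasma frequencies use. Keeping the printed figures would instead require 200 patients in the FAS, hence 200 / 0.9 = 222.2, or 223 enrolled, which the size of the discrepancy does not warrant.
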